### 7.3 13-CRA dosing

The appropriate dose will be delivered to each patient, according to the weight of the patient to deliver approximately 200 mg/m^2 13-CRA. Patients with a body weight of ≤12kg will receive a dose of 160 mg/m^2.

Each patient enrolled in the trial will receive 13-CRA in accordance with the dosing requirements.

Initial doses will be administered and checked by trained medical/nursing staff and recorded accurately in a controlled drug accountability log provided by the Sponsor. Remaining doses will be recorded by the parents/guardians in the diary card.

The Sponsor monitors will check the accuracy of the pharmacy and site for receipt of IMP, confirmation of receipt, pharmacy storage of the IMP packages, distribution records to the clinic and records of return to pharmacy and destruction of IMP. Any anomalies will be queried and clearly documented. All records will be maintained in the hospital pharmacy files with anonymised copies retained for the Sponsor trial master file.

#### **7.4 Packaging and labelling**

The Sponsor will provide sufficient quantities of IMP in accordance with Good Manufacturing Practice (GMP). The clinical trial supplies will be properly packaged and labelled in accordance with applicable local regulatory requirements.

#### **7.5 Preparation, handling and storage**

The IMP will be accounted for in a drug inventory and stored in a locked area in the pharmacy or in the hospital clinic until used in the trial. Storage information and batch characteristics will be supplied at the time of delivery. At the end of the trial the site will be contacted about the handling procedures for unused trial drug. The IMP will be destroyed by the site according to local procedures, this will be appropriately documented.

#### **7.6 Investigational medicinal product accountability**

The principal investigator at each site is responsible for ensuring the investigational medicinal product (IMP) accountability, including reconciliation of the IMP and maintenance of IMP records.

- Upon receipt of the IMP the principal investigator (or delegated pharmacist) will check for accurate delivery and acknowledge receipt by signing (or initialling) and dating the documentation provided by the supplier and faxing/scanning a copy back to the supplier. The original will be retained in the investigator/pharmacy file.
- The dispensing of the IMP will be carefully recorded on the appropriate drug accountability forms provided by the Sponsor. An accurate account will be made available for verification by the Sponsor monitor at each monitoring visit.
- IMP accountability records will include:
  - Release of the IMP by the supplier's Qualified Person.
  - Confirmation of IMP delivery to the trial site.
  - The inventory at the site of IMP provided by the supplier.
  - Details of pharmacy dispensing.
  - Administration of IMP to patients (in clinic, and on diary cards).
  - Destruction of excess IMP. All unused IMP will be destroyed by pharmacy personnel according to normal hospital policy, destruction will be clearly recorded, documented and checked by The Sponsor monitors.
  - Return to the supplier or alternative disposition of unused IMP.
- The principal investigator should maintain records that adequately document that:
  - Patients were treated with the dose specified in the protocol.
  - Preparation/administration and return/destruction of IMP was properly conducted.

Unused IMP must not be discarded without prior permission from the Sponsor or used for any purpose other than the present trial. IMP that has been dispensed must be accurately recorded for each patient.

The Sponsor monitor will periodically collect the IMP accountability forms and check all IMP data (both used and unused) prior to making arrangements for the return of unused IMP to the supplier or authorising their destruction by the trial site.

## **8 PREMATURE DISCONTINUATION FROM TRIAL**

### **8.1 Early Discontinuation of an Individual Patient**

Patients and their parent(s)/legal guardian will be informed that they have the right to withdraw from the trial at any time, without prejudice to their medical care and that they are not obliged to state their reasons. In addition, the investigator may remove a patient from the trial if, in the investigator's opinion, it is not in the best interest of the patient to continue in the trial.

Any withdrawal from the trial must be fully documented in the CRF and source.

The date of discontinuation from the trial and reason (where possible) for discontinuation will be recorded on the CRF and in the patient's medical records.

- Patients may be discontinued from the trial for the following reasons:
- Withdrawal of consent
- AE
- Deviation from protocol
- Other (to be specified on the CRF by the investigator if possible)

The data recorded (including PK samples) until the time of withdrawal will be used as part of the clinical trial unless the parent(s)/legal guardian or patient requests that it is not used.

Withdrawn patients may be replaced if the overall target number of samples has not been reached (i.e. a total of 150 samples).

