### **13.6 Adherence to the Protocol**

Protocol violations are any deviations from the procedures outlined in this document, for example, missed evaluations, incorrect timing of evaluations, non-compliance with IMP and intake of prohibited medications. It is the investigator's responsibility to make all reasonable efforts to avoid protocol violations in order to avoid possible exclusion of the patient from the trial and/or analyses.

All protocol violations will be reported immediately to the Sponsor and any action required, for example, discontinuation of the patient will be discussed. Evaluability of the patient(s) concerned will be performed by the Sponsor prior to the statistical analysis.

Any deviation from the protocol that has not been approved by The Sponsor and the IEC could result in a discontinuation from the trial of the site involved.

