7.2 Randomisation

Prior to the initiation of the trial 13-CRA, patients will be randomised to receive either liquid or extracted capsule formulation in “My –CRA month 1”. The patients will then cross-over to the alternative formulation in “My-CRA month 2”. After the trial if a patient requires additional cycles of 13-CRA, the patient will revert to standard 13-CRA therapy i.e. extracted capsules according to local practice.

Randomisation will be done centrally by Nova according to a randomisation list generated by the trial statistician, investigators will email (or telephone) Nova to receive randomisation details, this will be confirmed by email as “liquid first” or “extracted capsules first”, pharmacy contacts will also be notified.

8 Major Protocol Deviations

Protocol violations are any deviations from the procedures outlined in the protocol, for example, missed evaluations, incorrect timing of evaluations, non-compliance with investigation medical product (IMP) and intake of prohibited medications. It is the investigator’s responsibility to make all reasonable efforts to avoid protocol violations in order to avoid possible exclusion of the patient from the trial and/or analyses.

Major protocol deviations are defined as those deviations from the study protocol that may have the ability to impact the study results.

Major protocol deviations include (but are not limited to):

- Deviation from inclusion/exclusion criteria
- Withdrawal criteria met during the study but patient was not withdrawn
- Missed evaluations
- Incorrect timing of evaluations
- Prohibited concomitant medications
- Non-compliance with IMP

Where possible; major deviations will be programmatically generated. Listings of concomitant medications will be provided to the sponsor for review to identify prohibited medications prior to database freeze.

Major protocol deviations will result in exclusion from the pharmacokinetic population if they are considered likely to affect the determination of the pharmacokinetic parameters.

9 Analysis Populations

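### Sections 8.1 and 13.6 allow a child to be discontinued for any protocol deviation, so second-period data can be lost selectively, and the completer condition in 11.3.1 and SAP 9.1 can then drop that child from the PK population

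*Protocol*

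**What the plan says.** **Grounds for discontinuation.** Protocol 8.1 introduces its list with "Patients may be discontinued from the trial for the following reasons". One entry is "Deviation from protocol", separate from withdrawal of consent, adverse event and other. It carries no severity threshold.

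**What counts as a violation.** Protocol 13.6 treats any departure from the protocol's procedures as a violation and gives as examples "missed evaluations, incorrect timing of evaluations, non-compliance with IMP and intake of prohibited medications". On the response it says: "All protocol violations will be reported immediately to the Sponsor and any action required, for example, discontinuation of the patient will be discussed". It also asks investigators to "avoid protocol violations in order to avoid possible exclusion of the patient from the trial and/or analyses".

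**Withdrawal criteria.** Protocol 5.3 lists a positive pregnancy test, patient request and investigator discretion. Deviation is not among them.

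**Handling at analysis.** SAP section 8 says: "Major protocol deviations will result in exclusion from the pharmacokinetic population if they are considered likely to affect the determination of the pharmacokinetic parameters". Protocol 11.3.1 applies the same test of relevance to PK. However, 11.3.1 and SAP 9.1 also make completion of the trial a condition of the PK population, and 8.3 defines completion as finishing the 14-day follow-up after Month 2 dosing.

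**Data from discontinued patients.** Protocol 8.1 says: "The data recorded (including PK samples) until the time of withdrawal will be used as part of the clinical trial", unless the family objects. Sections 3.1 and 8.3 say that one PK sample is enough to enter the PK analysis.

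**The concern.** Adherence in this trial is partly an outcome. Section 1 describes children who are unwilling or unable to take capsules and variable dosing from extraction. Section 4.8 collects spitting out, vomiting, willingness and ease of administration as acceptability data. Apart from the clinic morning doses on PK days, doses are given at home and recorded on a diary card (6.3, 7.1). A refused or missed home dose is therefore both information on a secondary endpoint and a ground on which the child may be discontinued.

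A child removed during Month 1 never receives the second formulation. There is then no within-patient PK contrast, no Month 2 palatability score and no preference based on both products. The trial is open label, the Sponsor issues the allocation (6.1), and the Sponsor takes part in the discussion of what to do about a violation (13.6).

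The analysis-stage rules act only on deviations judged likely to affect PK. Removal under 8.1 and 13.6 has no such filter. Once a child is removed for a deviation that does not matter for PK, the completion condition can exclude that child from the PK population anyway.

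**Working it through.** The plan has no power calculation (11.3.2), so there is no figure of its own to reproduce. The check sets the rules side by side, then does three pieces of arithmetic.

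**1. One child under each rule.** Take a child who misses home doses in Month 1 in a way judged irrelevant to PK, and who is discontinued under 8.1.

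| Rule | Result for this child |
|---|---|
| 3.1, 8.3 | At least one sample, so in the PK analysis |
| 8.1 | Data up to withdrawal are used |
| SAP section 8 | Not excluded, because the deviation is irrelevant to PK |
| 11.3.1, SAP 9.1, read literally | Trial not completed, so not in the PK population |

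The first three agree and the fourth contradicts them. SAP section 2 puts the population PK analysis outside its scope, while SAP 9.1 says its population serves the primary variable. The documents do not settle which definition governs the model.

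**2. Loss of second-period data.** One removal among 12 to 20 patients loses 1/20 = 5% to 1/12 = 8.3% of the possible within-patient contrasts. The sample target does not protect these contrasts. At five samples per PK day (4.6, age two and over) and two PK days per period, a full patient gives 5 × 2 × 2 = 20 samples and a one-period patient gives 10. The target of 150 is met by 150/10 = 15 one-period patients with no cross-over contrast at all, which is within the limit of 20. Replacement under 8.1 is tied to that count.

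**3. Exposure ratio among completers (assumed inputs).** Let the true liquid/capsule ratio be 1.00. Let *s* be the between-patient SD of log exposure on each product, and *r* the correlation of acceptance with log exposure on the same product. Acceptance of the two products is taken as independent. In period 1 the least accepting fraction is removed: *q*L on liquid, *q*C on capsules. With normal acceptance, the mean among those kept is m(q) = φ(z_q)/(1 − q), which gives m(0.1) = 0.195, m(0.2) = 0.350, m(0.3) = 0.497 and m(0.4) = 0.644. Weighting the sequences equally:

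ratio = exp{ (s·r/2) × [m(qL) − m(qC)] }

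| s | r | qL, qC | Ratio |
|---|---|---|---|
| any | 0 | any | 1.00 |
| any | any | 0.1, 0.1 | 1.00 |
| 0.3 | 0.3 | 0.1, 0.3 | 0.99 |
| 0.3 | 0.6 | 0.1, 0.3 | 0.97 |
| 0.5 | 0.3 | 0.2, 0.4 | 0.98 |
| 0.5 | 0.6 | 0.1, 0.3 | 0.96 |
| 0.5 | 0.6 | 0.2, 0.4 | 0.96 |

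A simulation with the same inputs agrees (0.956 to 0.986 for unequal removal with *r* of 0.3 to 0.6). If removal were instead heavier on the liquid, the ratios would be the reciprocals, up to 1/0.956 = 1.05.

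**4. Preference (assumed inputs).** Suppose 14 of 20 families (70%) would prefer the liquid and 4 children are removed before crossing over. If *k* of those 4 would have preferred the liquid, the observed share is (14 − k)/16. That runs from 14/16 = 87.5% (k = 0) to 10/16 = 62.5% (k = 4). The direction depends on who is removed.

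**The case against.** The case on the other side is substantial.

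- **The clause is permissive.** The list in 8.1 follows the instruction to record a date and reason on the CRF, so it works at least partly as a set of reason codes. Section 13.6 says only that action will be discussed. This stands: a reader might infer that the plan does select the cross-over sample, but the text only permits it.
- **Missed samples do not measure acceptance.** A reader might treat a missed timed sample like a refused dose. Samples come from a central line already in place, only the 2 h and 6 h samples are mandatory, and PK-day morning doses are given in clinic. The argument fits missed or refused home doses only. A removal for a missed sample costs second-period data but says nothing about the product.
- **Timing makes removal before cross-over less likely.** The diary review in 4.10 is on Day 14, and monitoring usually follows Month 2 (13.2). This lowers the likelihood. It does not close the route, because 13.6 requires immediate reporting of violations.
- **The primary analysis is a pooled mixed-effects model.** It can use one-period data, so a complete-pairs figure such as √(16/13) = 1.11 for losing 3 of 16 pairs is not the planned standard error. This stands, but use of those data is not secure while 11.3.1 and SAP 9.1 require completion.
- **Imbalance would be visible.** SAP 11.1 tabulates the primary reason for discontinuation and major deviations by sequence. That shows the loss without recovering the data.
- **Investigator discretion remains.** The same child could still be withdrawn under 5.3. This is true, but that is a judgement about the patient and not a consequence of the deviation itself.

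**Conclusion.** The point holds as a wording and consistency defect with a plausible selective effect. Sections 8.1 and 13.6 allow a deviation of any kind to end participation, 5.3 does not list it, and the completion condition in 11.3.1 and SAP 9.1 conflicts with 3.1, 8.1 and 8.3.

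The firm consequences are the loss of second-period data (5% to 8.3% of possible contrasts per child at 20 to 12 patients) and acceptability and preference results that can be distorted in either direction.

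A reader might infer that relative bioavailability is biased. The documents do not support that as a finding. Bias in the ratio needs unequal removal between products and a link between acceptance and exposure, and the documents quantify neither. On the assumed inputs, with equal or heavier removal on capsules, the ratio is about 0.96 to 1.00 for a true 1.00. It is exactly 1.00 if either condition is absent.

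**What to change.** 1. Reconcile 8.1 and 13.6 with 5.3: remove deviation as a stand-alone reason in 8.1 and drop discontinuation as the example action in 13.6.
2. State that a deviation alone does not end trial data collection, that it is recorded, and that its effect is judged at analysis under 11.3.1 and SAP section 8.
3. Leave withdrawal of consent, adverse events, investigator discretion, the best-interest clause in 8.1 and the criteria for starting each cycle unchanged. The amendment should give no instruction on whether a given patient takes the next cycle.
4. Reconcile the completion condition in 11.3.1 and SAP 9.1 with 3.1, 8.1 and 8.3 so that data from a discontinued patient are kept, subject to the family's right to object and the existing test of relevance to PK. Say which definition governs the population PK model.

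The cost is a short protocol amendment and a matching SAP edit. The downside is that some imperfect profiles will be collected and must be adjudicated before analysis, which 13.6 and SAP section 8 already provide for.

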### **8.2 Early Discontinuation of the Trial**

If, in the opinion of the investigator, the clinical observations in the trial suggest that it might not be justifiable to continue, he may terminate the trial following consultation with the Sponsor. Alternatively, the Sponsor may give written notification to the investigator, regulatory authorities and ethics committees of the early discontinuation of the trial, including reasons.

In case of early discontinuation of the trial, safety assessments should be performed for each patient, as far as possible.

### **8.3 Patient and Trial Completion**

Patients will be considered to have completed the trial when the patient has completed the 14 day's follow up at the end of the My-CRA Month 2 dosing period. Patients who consent for the trial but who do not, for whatever reason, receive trial medication will be considered to be screening failures and their data will be recorded on a screening failure list. Patients who provide at least one pharmacokinetic blood sample for trial purposes will be deemed to have entered the trial and will be included in the PK analyses. All patients who receive trial medication will be considered for the safety analyses.

The trial will be considered to be completed 14 days after the last patient's has completed their My-CRA Month 2 dosing.

## **9 ASSESSMENT OF SAFETY**

Assessments of safety will be performed throughout the time that the patient is in clinic and for the 14 days that the patient receives medication at home (and for 14 days between dosing cycles

if adverse events are recorded in the diary card or are spontaneously reported by the patient to hospital staff) and 14 days from the time that the patient receives their last dose (Two weeks follow up after Day 14 of the treatment).

The on-going safety of the investigational medicinal product will be assessed through the recording, reporting and clinical assessment of baseline medical conditions, and adverse events recorded until discharged (and for 14 days follow up between cycles or post last dose if recorded in the diary card or spontaneously reported by the patient to hospital staff). Trial site personnel will report any adverse event (AE), whether observed by the research staff or reported by the patient.

Oro-praryngeal tolerability will be assessed at baseline and following dosing until a patient has completed the trial. Any local clinically relevant changes will be recorded as adverse events.

### 9.1 Definition of adverse events

An AE is any untoward medical occurrence in a patient or clinical trial patient administered a pharmaceutical product and which does not necessarily have a causal relationship with this treatment. An AE can therefore be any unfavourable and unintended sign (including an abnormal laboratory finding), symptom, or disease temporally associated with the use of an IMP, whether or not related to the IMP.

During the trial, any worsening of conditions, signs or symptoms noted from the time of consenting to take part in the trial will be recorded as an AE.

All AEs that occur (whether treatment related or not) will be recorded in the CRF throughout the duration of the visit (and for 14 days post dosing if recorded on the diary card or spontaneously reported to hospital staff).

As far as possible, each AE must be described by its duration (start and end time and date or ongoing), its frequency (single episode, intermittent, continuous), its severity (mild, moderate, severe - see section 9.2), a causality assessment (coexisting disease, concomitant medication, the IMP, or other cause), its relationship to the IMP (unrelated, unlikely, possibly, probably, definitely – see Section 9.2), whether this influenced the course of the IMP, whether it required specific action or therapy, and outcome.

All medical conditions present at baseline should not be considered as AEs unless these have worsened during the trial phase. In cases of surgical or diagnostic procedures the condition/illness leading to such a procedure is considered as the AE rather than the procedure itself.

### 9.2 Expected AE in 13-cis-retinoic acid recipients

Refer to Investigator Brochure.

### 9.3 Adverse events

Using the WHO toxicity criteria as a guide, the principal investigator will assess the severity of all AEs according to the following definitions:

- Mild:** The patient is aware of the event or symptom but it is easily tolerated.
- Moderate:** The patient experiences sufficient discomfort to interfere with or reduce his / her usual level of activity
- Severe:** Significant impairment of functioning – the patient is unable to carry out usual activities and/or the patient's life is at risk from the event.

The principal investigator will assess the relationship of AEs to the investigational medicinal product using the following definitions:

- Definite:** There is a definite clinical/biological relationship and time sequence between the onset of the AE and the administration of the investigational medicinal product.
- Probable:** A causal relationship is clinically/biologically highly plausible and there is a plausible time sequence between onset of the AE and administration of the investigational medicinal product and there is a reasonable response on withdrawal.
- Possible:** A causal relationship is clinically/biologically plausible and there is a plausible time sequence between onset of the AE and administration of IMP.
- Unlikely:** A causal relationship is improbable and another documented cause of the AE is most plausible.
- Unrelated:** A causal relationship can be definitively excluded and another documented cause of the AE is most plausible.

In case of a fatality the cause of death is captured as the AE and the death is its outcome.

## 10 PROCEDURE FOR RECORDING AND REPORTING ADVERSE EVENTS

Adverse event data will be recorded throughout the patient's stay in the clinic/hospital (and for 14 days post dosing if recorded in the diary card or if reported spontaneously to hospital staff).

### 10.1 Recording of adverse events in the case report form

As quality and precision of AE data collected is of key importance, the principal investigator or his designee should use the AE definitions provided in the above sections and follow the guidelines below when completing the AE pages of the CRF:

- Whenever possible recognised medical terms should be used to describe AEs rather than colloquialisms (e.g. 'influenza' rather than 'flu'). Abbreviations should be avoided. An adverse event term needs to be provided for each adverse event, preferably using the Short Name as listed in the Common Terminology Criteria for Adverse Events version 4 (CTCAE, current version 4.02), available online (10).
- AEs should be described using a specific clinical diagnosis rather than component signs and symptoms where possible (e.g. 'congestive heart failure' rather than 'dyspnoea, rales and cyanosis').
- Signs and symptoms that are considered unrelated to a specific disease or syndrome should be reported as individual AEs on the CRF (e.g. 'nausea' and 'vomiting' should be recorded separately and not as 'nausea and vomiting').
- Provisional diagnoses (e.g. 'suspected asthma') are acceptable but should be followed up by a definite diagnosis when/if finally available.
- AEs that are secondary to other events (e.g. 'sequelae or complications') should be identified by the primary cause. A primary AE, if clearly identifiable, generally represents the most accurate clinical term to be recorded on the AE pages of the CRF. The principal investigator should be invited to provide his/her own opinion of which is the primary AE.

